#### **4.6. Protocol Deviations**

The number and percentage of patients with at least one protocol deviation will be presented for the SP. Additionally, incidence by type of deviation will be presented; in these tabulations patients could be counted in more than one category if they have a deviation attributed to multiple categories. All protocol deviations will be presented in a data listing.

#### **4.7. Demographic and Baseline Characteristics**

Demographics and baseline characteristics will be summarized and presented for the SP for patients receiving only one dose, patients receiving two doses, and all patients combined. Age, height, weight, and body mass index (BMI) will be summarized using descriptive statistics (number of patients, mean, standard deviation, median, minimum, and maximum). Age will be calculated as the years between date of birth and date of informed consent, and will be rounded down to the nearest year. The number and percentage of patients in each gender, ethnicity and race category will also be presented. Additionally, for two-dose patients only, demographic and baseline characteristic data will be presented separately based on the time at which the second dose was administered. These statistics will be presented for the following groups. Each group will be displayed as a different column in the same table, in this order:

1. Patients receiving the second dose at Week 12
2. Patients receiving the second dose at Week 16
3. Patients receiving the second dose at Week 20
4. Patients receiving the second dose at Week 24
5. Patients Receiving the Second Dose after Week 24

OA background characteristic data and index knee characteristic data as collected on the CRF will also be tabulated for the SP for all patients combined. Time from primary diagnosis of OA in the index knee to Day 1 of the study in years (dose date – date of diagnosis + 1)/365.25, will be computed and presented descriptively. Additionally, for two-dose patients only, OA background characteristic data and index knee characteristic data will be presented separately based on the time at which the second dose was administered. These statistics will be presented

for the following groups. Each group will be displayed as a different column in the same table, in this order:

1. Patients receiving the second dose at Week 12
2. Patients receiving the second dose at Week 16
3. Patients receiving the second dose at Week 20
4. Patients receiving the second dose at Week 24
5. Patients Receiving the Second Dose after Week 24

For all time to diagnosis calculations, if only month and year of initial diagnosis is available, day will be imputed as 1 for calculations. If month and day are missing, the time from primary diagnosis will be computed as year of administration of study treatment minus year of diagnosis. If year is missing, time from diagnosis will not be computed.

All collected demographic, baseline characteristics, and medical history data will be provided in data listings, sorted by patient.

#### **4.8. Study Drug Exposure**

Details of study drug administration will be tabulated and presented for the SP by the following groups:

- First (and only) dose for patients receiving one dose
- First dose for patients receiving two doses
- Second dose for patients receiving two doses

The position of knee during injection, approach during injection, whether or not the entire contents of the syringe was injected, reason (if entire contents not injected), the numbing agent used, whether or not ultrasound guidance was used, volume of synovial fluid aspirated, and whether a 20 or 21-gauge needle was used will be presented.

Benefit from the initial dose of FX006 and patients with no major safety concerns during the initial dose period will be summarized for the Week 12 visit. In addition, patients clinically indicated to receive a second dose of FX006 and patients eligible for the second dose at Weeks 12, 16, 20 and 24 will be summarized, as well as the number of patients receiving the second dose at each of these visits. These data come from the “Repeat Dose Eligibility” CRF.

Patients receiving one dose and two doses and the visit at which the second dose was received will be summarized.

A summary of time to second dose will be displayed for patients receiving two doses. The median time to second dose will be estimated based on the 50th percentile of the Kaplan-Meier distribution. Additional summary statistics will be presented, including the 25th and 75th percentiles, and the corresponding 95% confidence intervals.

Additionally, repeat dose data will be presented separately by the following subgroups:

- K-L Grade 2, 3 and 4

- Prior IA steroid injection
- Unilateral/bilateral knee OA
- Prior index knee OA surgery or procedure

All study drug exposure data will be presented in a data listing.

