#### **9.4.2. Exposure**

Treatment exposure will be listed by study site and patient, and will be summarized by doses administered, as well as total exposure to FX006. Time between FX006 exposure (1st and 2nd doses) will be summarized.

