### 4.2. General Statistical Methods and Data Handling

#### 4.2.1. General Methods

All output will be incorporated into Portable Document Format (PDF) or Word files, sorted and labeled according to the International Conference on Harmonisation (ICH) recommendations, and formatted to the appropriate page size(s).

A list of tables, figures and listings to be generated, as well as mock shells, are provided in a separate document.

Tabulations will be produced for appropriate demographic, baseline, efficacy and safety parameters. Each table will present all patients combined, regardless of number of doses, unless otherwise specified.

For categorical variables, summary tabulations of the number and percentage within each category (with a category for missing data) of the parameter will be presented.

For continuous variables, the number of non-missing values (n), the mean, median, standard deviation (SD), confidence intervals (CI), minimum and maximum will be presented. Additional statistics may be presented for certain endpoints as described in the sections below.

Time to event data will be summarized using Kaplan-Meier Methodology using 25th, 50th (median), and 75th percentiles with associated 2-sided 95% confidence intervals, as well as percent of censored observations.

If performed, all statistical tests will be two-sided and a difference resulting in a p-value of less than or equal to 0.05 will be described as statistically significant and potentially informative.

All collected data will be presented in patient listings.

The sections below describe the intended analysis of the endpoints. Additional sensitivity analysis may be employed in the event of any unforeseen data anomalies or data issues not known at the time of writing this analysis plan.

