**Unscheduled visit windowing:**

If a patient receives their second dose of study medication at an unscheduled visit that is not  $>3$  weeks after Week 24, the dosing information and all other data collected at that visit will be mapped to the closest nominal visit, based on Rel Day Dose 1, even if data is already available in that visit. All data collected at the time of the second dose will be used for analysis. If data is available in the nominal visit, but was not collected at the unscheduled visit associated with the second dose, the data from the nominal visit will be used. If a patient receives their second dose at an unscheduled visit that is  $> 3$  weeks past Week 24, data from that unscheduled visit will not be used for time to second dose analyses or exploratory efficacy analyses involving two-dose patients.

Data collected at unscheduled visits that are not associated with the second dose will be mapped to the closest scheduled visit, but only if that data is not already available in that visit. Otherwise data will be summarized and presented according to the nominal visit as recorded on the Case Report Form (CRF).

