#### **4.5. Patient Disposition**

All patients who are enrolled will be accounted for in this study.

Patient disposition will be tabulated and include the total number of patients enrolled, treated, completed and early terminated, reason for early termination and the number in each patient population for analysis.

Subject completion will be presented overall and by the following categories:

1. At Week 12 (no clinical benefit)
2. At Week 24 (not clinically indicated to receive second injection)
3. At Week 52

Early termination will be presented overall and by the following time periods:

1. Prior to Week 12, which is the first visit for second dose eligibility
2. On or after Week 12, but prior to receiving second dose
3. On or after second dose and prior to 12 Weeks after second dose
4. On or after receiving the second dose but prior to Week 52

The following by-patient data listings will be presented:

- Study completion information including the reason for premature study discontinuation, if applicable.
- Inclusion/exclusion criteria not met.
- Repeat dose inclusion/exclusion criteria not met for all patients. If a patient receives a repeat dose on a visit where repeat dose inclusion/exclusion criteria were not met, that visit will be flagged.
- Repeat dose eligibility at Weeks 12, 16, 20 and 24.
- Patient inclusion in each of the analysis populations (SP, FAS, BP and PPIP). Reasons for exclusion from the PPIP will be presented.

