## 5. CHANGES TO PLANNED ANALYSES

In the original protocol the intended analysis was to compare the responses for those patients who received only a single dose to those patients who received two doses of FX006. During the study >90% of the patients enrolled have received a second dose, with approximately 10 patients only receiving one dose. This limited enrollment in a single dose does not adequately support making the protocol specified one-dose to two-dose comparisons for safety and exploratory efficacy meaningful. These comparisons have been eliminated from planned analyses.

According to the protocol, time to maximal pain relief response with WOMAC A (pain) following the first and second doses of FX006 would be examined using a Kaplan-Meier procedure. Instead, the time to second dose was examined using the Kaplan-Meier procedure as this provides a better indication of durability of first-dose response.

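### Kaplan-Meier time to second dose is offered as durability of first-dose response, but is summarised only in patients who received the second dose

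*SAP*

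**What the plan says.** Protocol 9.4.3 planned a Kaplan-Meier analysis of the time to maximal WOMAC A pain relief after each dose. SAP 5 replaces it: "Instead, the time to second dose was examined using the Kaplan-Meier procedure as this provides a better indication of durability of first-dose response".

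The replacement is specified only in SAP 4.8, Study Drug Exposure: "A summary of time to second dose will be displayed for patients receiving two doses". The Kaplan-Meier median and the 25th and 75th percentiles follow, with 95% confidence intervals. SAP 4.2.1 requires every time-to-event summary to show percentiles "as well as percent of censored observations". Neither document gives a censoring rule for time to second dose.

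SAP 4.2.9 adds that when a second dose is given at an unscheduled visit more than 3 weeks past Week 24, "data from that unscheduled visit will not be used for time to second dose analyses".

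Patients can finish with one dose in two planned ways (SAP 2.1 and 4.5): at Week 12 for lack of benefit, or at Week 24 when no second injection was indicated. Others may withdraw early. On numbers, SAP 5 reports that more than 90% of "the patients enrolled have received a second dose, with approximately 10 patients only receiving one dose".

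**The concern.** How long the first dose lasts is a question about patients given the first dose. The set in SAP 4.8 is defined by having had the event. Without censoring, the Kaplan-Meier curve is just the empirical distribution of re-dosing times, and it reaches zero at the last second dose however durable the response was. Its percentiles say when re-dosed patients were re-dosed.

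The missing patients differ in kind. Those who benefited and needed nothing more by Week 24 have the longest responses, and a late unscheduled second dose also marks a long interval. Leaving these out shortens the reported times. Patients who left at Week 12 without benefit had no response to time. Omitting them is defensible for duration of response, but not for a statement about everyone treated.

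At stake is an exploratory result to which SAP 5 gives an efficacy meaning. A reader could take its median as the typical duration of benefit after one injection.

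**Working it through.** **The plan's own figures.** The documents give no result for time to second dose. The enrolment figure reproduces: 200 × 0.66 × 0.75 = 99, against a target of 100 two-dose completers. About 10 one-dose patients among the planned 200 is 5%, so r = 190/200 = 0.95 re-dosed, consistent with SAP 5's more than 90%. Actual enrolment is not stated, so r = 0.90 is the other end of the range.

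**Formula.** If a fraction r of treated patients is re-dosed and nobody else withdraws before Week 24, the all-treated cumulative proportion re-dosed by a visit is r × (cumulative share of two-dose patients re-dosed by that visit). The all-treated quantile p is therefore the two-dose quantile p/r.

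- r = 0.95: 0.25/0.95 = 26.3%, 0.50/0.95 = 52.6%, 0.75/0.95 = 78.9%.
- r = 0.90: 27.8%, 55.6%, 83.3%.

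The all-treated proportion still without a second dose at Week 24 is 1 − r, or 5% to 10%. The planned display shows 0%.

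**Nominal weeks.** The documents do not give the split of second doses over Weeks 12/16/20/24, so these splits are assumptions. Quartiles are shown as 25th/50th/75th percentiles, in weeks.

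| Split (%) | Two-dose only | All treated, r = 0.95 | All treated, r = 0.90 |
|---|---|---|---|
| 70/15/10/5 | 12/12/16 | 12/12/16 | 12/12/16 |
| 40/25/20/15 | 12/16/20 | 12/16/20 | 12/16/20 |
| 60/20/12/8 | 12/12/16 | 12/12/16 | 12/12/20 |
| 52/26/12/10 | 12/12/16 | 12/16/20 | 12/16/20 |

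Example, last row at r = 0.95: the cumulative proportions are 0.95 × 0.52 = 0.494, 0.95 × 0.78 = 0.741 and 0.95 × 0.90 = 0.855. The median passes from Week 12 to 16 and the third quartile from Week 16 to 20. This split was chosen to fall inside the narrow bands where a move occurs (50 to 52.6% and 75 to 78.9%).

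**Actual days.** SAP 4.8 states no time unit, and protocol Table 1 allows visits ±7 days. Take Week 12 as day 84 and assume dosing days are uniform over each window.

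- 52/26/12/10, r = 0.95. Two-dose median: 77 + 14 × 0.50/0.52 = 90.5. All-treated median: 105 + 14 × (0.5263 − 0.52)/0.26 = 105.3, a shift of about 15 days. The third quartile goes from 117.4 to 134.1, about 17 days.
- 60/20/12/8, r = 0.95. Third quartile: 105 + 14 × 0.15/0.20 = 115.5 becomes 105 + 14 × 0.1895/0.20 = 118.3, about 3 days.
- In the other two splits at r = 0.95, no quartile moves by more than 4 days.
- At r = 0.90 the largest shift in these four splits is about 22 days (52/26/12/10, third quartile: 117.4 to 139.2).

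**Why plain censoring is not enough.** Take 200 treated and 10 with one dose. If all 10 leave at Week 12 for lack of benefit and are merely censored, 1 minus Kaplan-Meier reaches 1.00 at Week 24, although 190/200 = 0.95 were re-dosed. With 5 leaving at Week 12 and 5 at Week 24 it is about 0.97.

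**The case against.** The strongest reply is that this is an exposure summary. Protocol 9.4.2 asks for the time between first and second doses, which exists only for two-dose patients. That stands, and the interval should be kept. It does not answer SAP 5, which gives the same summary an efficacy meaning.

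A second reply is that the information is already planned. SAP 4.8 counts patients re-dosed at each visit and one- and two-dose totals, SAP 4.5 counts completers and early terminations, and SAP 4.9.1.4 uses WOMAC area under the effect curve as its own indicator of durability. A reader could rebuild the all-treated proportions by hand. This limits the harm but leaves the reported percentiles and confidence intervals as they are.

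Third, an all-patient analysis may have been intended. The Kaplan-Meier sentence in SAP 4.8 does not repeat the restriction, and SAP 4.2.1 expects censoring. The 0% censored follows from the text as written, not from any statement of intent. Without a censoring rule, however, the wider analysis is not specified.

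Fourth, re-dosing is not loss of response. It cannot occur before Week 12 in the planned schedule, and it depends on benefit, safety, compliance and joint judgement by patient and investigator (protocol 7.4.3). This is correct: an all-treated estimate is still only a proxy.

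Some stronger inferences are not supported:

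- A reader might infer that SAP 4.2.9 conflicts with the SAP 4.7 column headed "Patients Receiving the Second Dose after Week 24". Describing those patients at baseline while leaving some out of this analysis is consistent, and SAP 4.2.9 concerns only late doses at unscheduled visits.
- A reader might extend the point to the first-dose column for all patients in SAP 4.9.1.1 and 4.9.1.3. Its stopping rule is printed with it and the number of patients is shown, so that is at most a labelling preference.

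**Conclusion.** The mismatch is real on the text. The summary describes re-dosing times among the re-dosed, and SAP 5 presents it as durability of first-dose response.

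The size is small. At about 95% re-dosed, quartiles shift by nothing to one visit in nominal weeks in the splits tried, or by under a day to a little over two weeks in actual days. Near 90% re-dosed the day shift can reach about three weeks. These figures assume about 200 treated, no other withdrawal before Week 24, and visit splits that the documents do not give.

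A reader might infer that durability is materially misstated in a known direction. The documents do not support that. Among responders the omissions shorten the reported times, but no-benefit exits pull the other way for all treated patients, and the make-up of the roughly 10 one-dose patients is not stated. Nor is a four-week jump to be expected as a rule: it needs nominal visit timing and a split inside a narrow band.

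The analysis is exploratory and the primary safety objective is unaffected. The change should be made because the wording claims more than the estimate can carry.

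**What to change.** In SAP 4.8, estimate time to second dose in all patients given dose 1:

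- Censor at Week 24 those who complete without a second dose.
- Treat Week 12 exit for no benefit as a competing event, or simply report the cumulative proportion re-dosed by each visit out of all treated.
- State how other withdrawals and late unscheduled second doses are handled, and whether time is in nominal weeks or actual days.
- Report the percent censored.

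Describe the result as time to re-dosing under the protocol's eligibility rules, a proxy for durability. Keep the two-dose-only interval as the exposure summary of protocol 9.4.2. At minimum, delete the durability rationale from SAP 5.

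The cost is SAP wording and minor programming, since the dates and counts are already collected. With so few one-dose patients the numbers will change little, and a rule for other withdrawals has to be written. The minimum version costs one sentence.

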## 4.9. Exploratory Efficacy Analyses

The examination of efficacy is exploratory in this study. All efficacy analyses will be conducted using the FAS.

### 4.9.1. WOMAC

The following WOMAC scales/questions will be analyzed:

- WOMAC A (pain subscale)
- WOMAC B (stiffness subscale)
- WOMAC C (function subscale)
- WOMAC (total)

For the WOMAC subscales, scores at each assessment time point (baseline, Week 4, Week 8, Week 12, etc.) will be calculated as the average of the responses to all questions in the subscale. Total score will be computed as the average of the average responses on each of the subscales (e.g. Average A + Average B + Average C divided by 3). This will provide a uniform scoring of 0 to 4 for each subscale and easier interpretation. Imputation rules are as presented in section 4.2.8.

Eligibility in this trial is based upon the WOMAC A total sum score at Screening and Day 1/baseline (maximum score of 20). This will be provided for all visits in a data listing.

#### 4.9.1.1. Descriptive statistics, all patients

Descriptive statistics will be presented for the following groups. Each group will be displayed as a different column in the same table, in this order:

1. Patients receiving the second dose at Week 12
2. Patients receiving the second dose at Week 16
3. Patients receiving the second dose at Week 20
4. Patients receiving the second dose at Week 24
5. Patients receiving only one dose
6. All patients, first dose – all patients through patient discontinuation, study completion (through Week 12 or Week 24), or until the second dose is received (whichever happens sooner)

Descriptive statistics (number of observations, unadjusted mean, SD, median, minimum and maximum) will be presented for WOMAC A, WOMAC B, WOMAC C and WOMAC total by visit (baseline through Week 52). Change from baseline will also be presented. For the change from baseline calculation, baseline is the WOMAC result obtained on Day 1 prior to first dose.

The adjusted change from baseline will also be presented. This will be done using a longitudinal mixed effects model for repeat measures (MMRM) with fixed effects for study time point, study site and baseline score. Patient will be the random effect. The analysis will include all study visits of data. This model assumes that missing values are missing at random. This model will be run separately for each group and for WOMAC A, WOMAC B, WOMAC C and WOMAC total.

This model will be run using the SAS/STAT® PROC MIXED procedure with an unstructured correlation matrix to model the within-subject errors. If the unstructured covariance matrix does not converge when fitting the mixed model, further investigation into the most appropriate correlation matrix will be conducted. The final selection of the correlation matrix to be used in fitting the mixed model will be fully documented in the results section of the CSR.

This model will provide the baseline adjusted Least Square Means (LSM) at each visit with the corresponding standard error (SE) and associated 95% CI.

Sample SAS code that can be used to implement the mixed effects analysis is provided below:

```
proc mixed data=dsin1 method=reml;  
  by group;  
  class subjid group avisitn siteid;  
  model chg= base group avisitn siteid;  
  repeated avisitn /type=un subject=subjid;  
  lsmeans group/diff=control ('1') cl;  
run;
```

In the above code, "group" refers to the groups listed below. The model will be run for each group separately.

A line plot presenting LSM change from baseline in WOMAC score over time will be produced. Each group will be plotted on a separate line with SE bars. Jitter will be used as needed to distinguish overlapping data.

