## 2. SYNOPSIS

Title of Study: An Open-label Study to Assess the Safety of Repeat Administration of FX006 to Patients with Osteoarthritis of the Knee
Study Centers: Approximately 20 centers
Study Phase: 3b
Objectives: The primary objective of this study is to assess the overall safety and general tolerability of repeat administration of FX006 (two doses of 32 mg FX006) in patients with symptomatic osteoarthritis (OA) of the knee. Exploratory objectives of this study include the following: 

• examine efficacy signals for sustained pain reduction following two doses of 32 mg FX006.

• collect synovial fluid samples to enable potential future examination of synovial fluid biomarkers that may contribute to the pathogenesis of OA and/or be associated with responsiveness to FX006 treatment.

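### The adjusted WOMAC model is very unlikely to be supportable in the one-dose group, and its sample code does not request the visit means that the text promises

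*SAP*

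**What the plan says.** SAP 4.9.1.1 defines six groups: four by week of second dose (12, 16, 20, 24), patients with one dose only, and all patients during their first dose. The adjusted change from baseline comes from a mixed model "with fixed effects for study time point, study site and baseline score", "with an unstructured correlation matrix to model the within-subject errors". On data: "The analysis will include all study visits of data". On fitting: "This model will be run separately for each group and for WOMAC A, WOMAC B, WOMAC C and WOMAC total". That is 6 × 4 = 24 separate fits. SAP 4.9.2 sends KOOS QOL through a similar analysis.

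The text promises baseline-adjusted least-squares means with standard error and 95% CI at each visit, then a line plot of them over time by group. The sample code runs under a `by group` statement, keeps `group` in the model, and asks for "lsmeans group/diff=control ('1') cl".

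On failure to fit: "If the unstructured covariance matrix does not converge when fitting the mixed model, further investigation into the most appropriate correlation matrix will be conducted".

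SAP section 5 reports that more than 90% of patients received a second dose, "with approximately 10 patients only receiving one dose", and for that reason withdraws the one-dose versus two-dose comparisons. The Protocol synopsis gives "Approximately 20 centers". SAP 2.1 has one-dose patients finishing at Week 12 (no benefit; three post-baseline visits) or Week 24 (six visits), and two-dose patients followed at 13 visits to Week 52.

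**The concern.** Section 5 treats the one-dose group as too small to compare, yet 4.9.1.1 still fits it alone with a site effect and the most heavily parameterised covariance available. Once site and baseline are fitted to about 10 patients over many sites, little between-patient information is left to estimate a 6 × 6 covariance matrix. The standard errors and intervals in that column, and the error bars on that plot line, would then mean little. If a small timing group also fails, the covariance would be chosen after the failure, with no order set in advance.

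The code problem is independent of group size. Whoever follows the block as written cannot fill the by-visit table or draw the plot.

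**Working it through.** **The plan's own figure.** The SAP gives no number for this model. Its only sizing figure does reproduce: 200 × 0.66 × 0.75 = 99 patients completing after two doses, against the stated 100.

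**Parameter count, one-dose group.** Inputs: n = 10 (SAP 5), t = 6 visits (SAP 2.1), 20 centres (Protocol synopsis).
- Unstructured covariance: t(t + 1)/2 = 6 × 7/2 = 21.
- Fixed effects without site: 1 intercept + 5 visits + 1 baseline = 7.
- Expected occupied sites if each patient is equally likely to come from any site: 20 × (1 − 0.95^10) = 8.03, adding about 7 site parameters.
- Total: about 7 + 7 + 21 = 35 parameters, for at most 10 × 6 = 60 observations.

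**Condition for a non-singular fit.** Site and baseline have no visit interaction, so with S occupied sites they use S + 1 between-patient degrees of freedom and leave n − S − 1. If t exceeds that number, some weighted combination of the visits is fitted exactly, its residual variance goes to zero and the matrix is singular. With complete data the requirement is n − S − 1 ≥ t. For n = 10 this means S ≤ 3 at six visits and S ≤ 6 at three visits.

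**Exact occupancy probabilities, n = 10.** The spread over sites is an assumption, so a range is shown.

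| Equally likely sites | Expected occupied | Expected df (10 − S − 1) | P(df ≤ 1) | P(non-singular), 6 visits | P(non-singular), 3 visits |
|---|---|---|---|---|---|
| 20 | 8.03 | 0.97 | 71% | <0.0001 | 0.07 |
| 15 | 7.48 | 1.52 | 50% | <0.0001 | 0.17 |
| 10 | 6.51 | 2.49 | 15% | 0.0007 | 0.49 |

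The three-visit column applies only if every one-dose patient stopped at Week 12, when the covariance has 3 × 4/2 = 6 parameters. With 20 sites there is a 33% chance of zero or fewer df. With 12 patients instead of 10, the six-visit probability is 0.0006, 0.004 and 0.045 for 20, 15 and 10 sites.

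**Numerical check.** REML fits to simulated data (n = 10, six visits, one data set per setting) gave a collapsing covariance at 4, 5 and 8 sites (smallest-to-largest eigenvalue ratio about 3e-6, 5e-8 and 9e-5). It stayed non-singular at 3 sites (2e-2). When half the patients stopped at Week 12, the fit collapsed even with no site effect (9e-8). Removing site alone may therefore not be enough.

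**Effect on the interval.** As an illustration, the 95% t-multiplier is 12.7 at 1 df and 2.3 at 8 df (10 − 2, no site term). This bears on the tabulated CIs. The plot carries SE bars, so it does not apply there.

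**Two-dose timing groups.** t = 13 gives 13 × 14/2 = 91 covariance parameters and needs n − S − 1 ≥ 13. With at most 20 sites this always holds once n ≥ 20 + 1 + 13 = 34. Under the equal-spread assumption with 20 sites and complete data, the chance of falling short is 29% at n = 30 and 98% at n = 25. The documents do not give the group sizes.

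**Code.** Within one `by group` run, `group` has a single level. It is aliased with the intercept, `lsmeans group` returns one mean averaged over visits, and the contrast with a control has nothing to compare. No statement requests means for `avisitn`.

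**The case against.** A reader might infer that the one-dose visit means cannot be estimated at all. The documents do not support that. With additive site and visit effects the visit means are generally estimable; what fails is the unstructured covariance, and with it the standard errors and intervals. How badly depends on the sites of these patients and on how many reached Week 24, and neither is reported. If all stopped at Week 12 and came from few sites, the fit could work.

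A reader might also infer that the two-dose models fail. That does not follow either. If about 200 were enrolled and 90% re-dosed, the average timing group is 200 × 0.9/4 = 45, above the threshold of 34. Groups may be unequal, so a small one could still be at risk, but this is conditional.

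The consequence is limited. Efficacy is exploratory, and unadjusted statistics by visit are given for the same columns. The one-dose versus two-dose comparison has been withdrawn. The main two-dose analyses in SAP 4.9.1.2 pool all two-dose patients and use at most three visits per dose. The code is labelled as a sample, and the text makes the intended output clear.

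All of this stands and bounds the point. It does not remove it: the fallback addresses only the covariance, names no alternatives, and leaves site in the model. The SAP also treats its code as working instructions, since 4.9.1.4 says that the 4.9.1.2 sample code will be used.

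**Conclusion.** The point holds in bounded form. For the one-dose group, the specified model is very unlikely to be supportable: the probability of a non-singular fit over six visits is below 0.001 for 10 patients across 10 to 20 equally likely sites. It rises to 0.07–0.49 only if every such patient stopped at Week 12. This assumes about 10 patients, even spread over sites and complete data to the last visit; patients stopping at different weeks make the six-visit fit harder. The affected results are the adjusted SEs and 95% CIs of one column and one plot line per score.

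For two-dose timing groups the risk depends on sizes the documents do not give, and it should not be stated as a finding about those groups. The code error rests on no assumption. Neither part touches the primary safety objective.

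**What to change.** 1. In the 4.9.1.1 code, remove `group` from MODEL and LSMEANS and request `lsmeans avisitn / cl` within each BY group. This returns up to 6 visit means for one-dose patients and 13 for each two-dose group. At the same time, reconcile the text's patient random effect with code that has only a REPEATED statement.
2. For the one-dose group, report the unadjusted descriptive statistics only and omit its LSM line. Alternatively, drop site and use a simple covariance: compound symmetry gives 7 fixed + 2 covariance = 9 parameters, against about 35 now.
3. Pre-specify an ordered list of covariance structures and a rule for dropping site in small timing groups, for example when patients minus occupied sites minus 1 is below the number of visits.

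One pooled model of the five mutually exclusive groups, with group-by-visit and `lsmeans group*avisitn`, is an acceptable option but is not required. It imposes a common covariance and baseline slope, and one-dose cells after Week 24 must be marked as not estimated. The overlapping all-patients first-dose set would stay separate.

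The cost is a few lines of SAP text and a corrected code block. No data collection changes. The descriptive option gives up an adjusted estimate for about 10 patients.
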